16.1 Protection of human subjects	30

17.	Study timelines	31
18.	Administrative and legal obligations	31
18.1	Study amendments and study termination	31
18.2	Study documentation and archive	31
18.3	Ethical and regulatory approvals	32
18.4	Ethical issues	32
19.	Communication of study results	32
20.	Study support.....	33
21.	References	34
22.	Appendices.....	36

1. List of tables

Table 1. Study amendments	14
Table 2 Study variables	21
Table 3 Confidence limits for different sample sizes and mean doses of RAASi achieved	25
Table 4 study timelines	31

2. List of abbreviations

Abbreviation	Definition
ACEi	Angiotensin converting enzyme inhibitor
ACR	albumin:creatinine ratio
AE	Adverse event
ADR	Adverse drug reaction
ARB	Angiotensin receptor blocker
CI	Chief Investigator
95% CI	95% confidence interval
CKD	Chronic kidney disease
EDC	Electronic data capture
eDCF	Electronic data collection form
eGFR	Estimated glomerular filtration rate
ENCePP	European Network of Centres for Pharmacoepidemiology and Pharmacovigilance
GAfREC	Governance Arrangements for Research Ethics Committees
GCP	Good Clinical Practice
GP	General Practitioner
HF	Heart failure
HRA	Health Research Authority
ISPE	International Society for Pharmacoepidemiology
LVEF	Left ventricular ejection fraction
MHRA	Medicines and Healthcare Products Regulatory Agency
MRA	Mineralocorticoid receptor antagonist
NIHR	National Institute for Health Research
NHS	National Health Service
PAS	Patient Administration System
PCR	protein:creatinine ratio
PI	Principal investigator

Abbreviation	Definition
R&D	Research and Development
RAASi	Renin–angiotensin–aldosterone system inhibitors
REC	Research Ethics Committee
SADR	Serious adverse drug reaction
SDV	Source data verification
STROBE	Strengthening the Reporting of OBservational Studies in Epidemiology
T2DM	Type 2 diabetes mellitus
UK	United Kingdom

3. List of definitions

Baseline: test result in medical records with date closest to and before the index event and within 12 months of the index event, or on the same date as the index event

Chronic Kidney Disease (CKD) stages 3 and 4: estimated glomerular filtration rate (eGFR) $>14\text{ml}/\text{min}/1.73\text{m}^2$ and $<60\text{ml}/\text{min}/1.73\text{m}^2$

Enrolment period: the 12 month period between 01 January 2016 and 31 December 2016

Heart failure (HF): presence of reduced ejection fraction and left ventricular ejection fraction (LVEF) $<40\%$

Index event: first prescription of RAASi during the enrolment period

Maximum tolerated dose: highest dose of RAASi (or MRA) recorded in medical records during observation period

Observation period: the 12 month period from index event

Target dose: as stated in medical records, national or international clinical guidelines or Summary of Product Characteristics (SPC) if not recorded in medical records (see Appendices)

Type 2 diabetes (T2DM): Chronic metabolic disorder that results in hyperglycaemia (high blood glucose levels) due to the body's inability to produce enough insulin or lack of ability to utilise the insulin being produced (insulin resistance). Confirmed diagnosis in medical records

4. Study synopsis

Title	
SoMoR – UK (Study of Management of RAASi in UK)
 
A multi-centre, retrospective observational study on renin-angiotensin-aldosterone system inhibitors (RAASi) management in patients treated for chronic kidney disease alongside heart failure and/or type 2 diabetes mellitus.

Background and rationale for study	
In order to improve renin-angiotensin-aldosterone system inhibitors (RAASi) treatment by increasing the proportion of patients who achieve target doses according to clinical guidelines, the maximum tolerated doses that are currently achieved need to be determined. This study will therefore describe the characteristics and treatment outcomes of patients with CKD and at least one of the following: heart failure (HF) and/or type 2 diabetes mellitus (T2DM) and who receive RAASi in the real world UK NHS setting but do not achieve target dose. The maximum tolerated doses achieved by these patients and the length of time on these doses will be reported.

Objectives	
Primary objective
 
 1. To describe doses of RAASi prescribed to patients with CKD in the UK NHS setting 
Secondary objectives
 
 1. To describe doses of mineralocorticoid receptor antagonist (MRA) prescribed to patients with CKD and HF 2. To describe other drug types concomitantly prescribed for CKD and/or HF in patients treated with RAASi 3. To describe clinical outcomes associated with RAASi treatment 4. To describe the demographic and clinical characteristics of patients treated with RAASi and do not achieve target dose, at initiation of treatment
Hypothesis statement	
This is a descriptive study and therefore an a priori hypothesis will not be tested.

Study design	
This is a multi-centre, retrospective observational study to take place in NHS secondary care centres in the UK.

Data source(s)	
Patient-level data recorded in primary and secondary care settings will be collected. Patient demographic data, and clinical data on prescribing patterns and patient management, will be collected from each centre.
 
Data will be extracted from the electronic Patient Administration System (PAS), service databases and electronic (or paper) medical

	
notes by the NHS clinical care teams or a pH Associates researcher. The extracted data will then be entered into the study database using a web-based, secure data capture and data management tool ('MACRO'). An electronic data collection form (eDCF) will be created to facilitate the entry of data into the database.
 
Data management
 
Source data verification (SDV) will be carried out to monitor data quality on a subset of all data submitted (typically 10% of records from each centre).

Number of centres	
Based on experiences with similar studies, it is estimated that between five and ten centres will be required to recruit the proposed number of study participants. pH Associates will liaise with Vifor to recruit the optimal number of centres and participants to achieve the study objectives. Centres will be recruited to provide as geographically representative a study sample as possible across the UK.

Number of subjects	
The analyses will be descriptive and therefore the required sample size will be estimated based on precision instead of statistical power. It is expected that approximately 100 patients will be sufficient to generate reliable results, as determined by relatively narrow confidence intervals. The number of patients in the study will be allocated as follows: 50% with CKD and HF and 50% with CKD and T2DM. This distribution includes patients with CKD, HF and T2DM.

Study time period	
Patients will be eligible for study enrolment if they were initiated on RAASi treatment during the 12 month period from 01 January 2016 to 31 December 2016.
 
The retrospective observation period for each patient will be 12 months from their RAASi initiation date.

Patient selection	
This study will investigate the prescribing of RAASi in the real world UK NHS setting in patients with chronic kidney disease (CKD) stage 3 or 4 who do not achieve target RAASi dose during the observation period and have at least one of the following:
 
 • heart failure (HF) • type 2 diabetes mellitus (T2DM) 
Where:
 
 • CKD stage 3 or 4 is defined as estimated glomerular filtration rate (eGFR) >14ml/min/1.73m² and <60ml/min/1.73m² • HF is defined as presence of reduced ejection fraction and left ventricular ejection fraction (LVEF) <40% • T2DM is defined as a confirmed diagnosis in medical records

	
The NHS clinical care team will identify eligible patients based on the following:
 
Inclusion criteria
 
 • Diagnosed with CKD stage 3 or 4 and at least one of the following: HF and/or T2DM • Prescribed a RAASi for the first time at an outpatient CKD and/or HF clinic between 01 January 2016 to 31 December 2016 ('the enrolment period') • Aged ≥ 18 years when prescribed a RAASi for the first time during the enrolment period • Patients who do not achieve target dose of RAASi during the observation period • With ≥ 12 months follow up data during the observation period • Consent to researcher access to their medical records for study data extraction (living patients only) 
Exclusion criteria
 
 • Received heart or kidney transplant before or during the observation period • Diagnosed with type 1 diabetes mellitus or acute kidney injury • Diagnosed with metastatic, late-stage or end-stage cancer with < 12 months life expectancy • Hospital medical records are unavailable for review • Enrolled in a blinded clinical trial of an investigational medicinal product during the observation period

Study endpoints
	
Endpoints will be analysed by drug type and patient group (CKD and HF, CKD and T2DM, CKD and HF and T2DM), where relevant.
 
Primary endpoint
 
 1. Mean maximum tolerated daily dose of RAASi achieved (as percentage of target dose) 
Secondary endpoints
 
 2. Length of time on maximum tolerated daily dose of RAASi 3. Proportion of patients with HF who receive RAASi and MRA 4. Maximum tolerated daily dose of MRA achieved in patients with HF 5. Length of time on maximum tolerated daily dose of MRA in patients with HF 6. Distribution of other drugs concomitantly prescribed for CKD and/or HF to patients treated with RAASi, by drug type 7. Proportion of patients with elevated serum potassium level (> 5.1 mmol/L, > 5.5 mmol/L or > 6.0 mmol/L) during the observation

	
period
 
 8. Number of episodes per patient with elevated serum potassium level (>5.1 mmol/L, >5.5 mmol/L or >6.0 mmol/L) 9. Change in mean serum potassium level (from index date to last result during observation period) 10. Change in mean serum creatinine level (from index date to last result during observation period) 11. Change in mean urine protein level (from index date to last result during observation period) 12. Change in mean blood pressure level (from index date to last result during observation period) 13. Proportion of patients who stop RAASi treatment at least once during the observation period 14. Reason(s) for changing RAASi dose or stopping RAASi treatment, where relevant 
Other measures
 
Patient demographic and clinical characteristics at the time of RAASi initiation will also be reported, including age, sex, ethnicity, length of time since diagnosis of CKD (and HF and/or T2DM if relevant), eGFR, LVEF (if diagnosed with HF), and comorbidities.


Statistical considerations
	
Given the descriptive nature of the study, results will be reported in terms of precision (95% confidence intervals, CIs) and not statistical power.
 
Data from all centres will be pooled for analysis. Categorical data will be described by the number (n) and percentage (%) of patients in each category. Continuous data will be described by number of observations, mean and standard deviation (SD) for normally distributed data or median and interquartile range for non-normally distributed data, and minimum and maximum values where relevant. Missing and invalid observations will be tabulated as a separate category. Rates will be reported with 95% CIs.

Regulatory, ethical and administrative obligations
	
This is an observational research study where only patients who consent (if living) for their medical records to be accessed for the purpose of the study will be included in the study. For deceased patients study data will be extracted from medical records by a member of the direct care team to preserve patient confidentiality in absence of consent from these patients.
 
There will be no change to the clinical management of patients as a result of taking part in the study. No additional patient investigations or tests will be required.
 
Data collection will be carried out by either the clinical care team at

	
each centre or a pH Associates researcher. Therefore, this study will be submitted for NHS Research Ethics Committee (REC) approval in line with the harmonised edition of the Governance Arrangements for Research Ethics Committees (GAfREC). Local management approval will be obtained via the Health Research Authority (HRA) and Trust/Health Board Research and Development (R&D) departments.
 
All electronic data files will be securely stored on a password-protected internal UK-based server at pH Associates and all study-related documents will be kept in a locked cupboard when not in use. Access to the study database will be restricted (by password protection) and only granted to pH Associates staff who are directly involved with the study.

--	---

5. Study amendments and protocol deviations

All amendments to the protocol will be documented in Table 1. Protocol deviations will be documented in a Protocol Deviation Log.

Table 1. Study amendments

Amendment number	Date of amendment	Description	Reason for amendment
1	21 st March 2018	References to mineralocorticoid receptor antagonists (MRAs) updated in the following sections: 3. List of definitions (page 8), 4. Study synopsis (pages 9 and 11), 6. Background (page 15), 7. Aim and objectives (page 16), 9. Study design and methodology (pages 20 and 23).	Only spironolactone was previously included in the protocol but data on eplerenone will also be collected in the study.
2	21 st March 2018	Removal of exclusion criteria for "Received dialysis during the observation period". The following sections have been updated: 4. Study synopsis (page 11) 9. Study design and methodology (page 18).	Although very few patients with CKD stage 3 or 4 (study population of interest) will receive dialysis, excluding these patients may introduce bias and therefore they should not be excluded from the study.
3	21 st March 2018	Secton 17. Study timelines updated (page 31).	Updated as timelines for study activities (but not study completion date) have changed since the last version of the protocol in December 2017.

6. Background and rationale

It is estimated that approximately 6% of the population of England aged 16 years or older have (diagnosed or undiagnosed) chronic kidney disease (CKD) stage 3 to 5¹. Renin–angiotensin–aldosterone system inhibitors (RAASi) are commonly prescribed to patients with CKD, with or without heart failure (HF) and with or without diabetes mellitus. RAASi include the following drug types: angiotensin converting enzyme inhibitors (ACEi) and angiotensin receptor blockers (ARBs).

RAASi are used to delay disease progression (e.g. end-stage renal failure) and to prevent major cardiac events. As such, they can maintain/improve and prolong patients' quality of life. The introduction and maintenance of RAASi treatment is well established as part of recommended treatment pathways for CKD and HF^{2–4}. However, patients treated with RAASi are at risk of elevated serum potassium levels (hyperkalaemia), through impaired renal function and/or side effect of the drugs. As hyperkalaemia can be a serious medical emergency, leading to organ failure and resulting in death, patients often do not achieve the target doses that are required for optimal clinical benefit due to clinician concerns about potential, or actual episodes of, hyperkalaemia^{5–7}. Patients with HF are typically also treated with a mineralocorticoid receptor antagonist (MRA), such as spironolactone or eplerenone.

Patients with HF are recommended to be treated with a MRA as well, to reduce symptoms of HF such as fluid retention and to lower mortality risk⁸. MRAs add to the risk of hyperkalaemia. As such, patients with CKD and HF who are treated with RAASi may receive a below target dose of MRA or not receive MRA treatment at all, which hampers the management of HF in this patient group^{9,10}.

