6.1 Rationale for study

In order to improve RAASi treatment in terms of increasing the proportion of patients who achieve target doses according to clinical guidelines, the maximum tolerated doses that are currently achieved need to be determined. This study will therefore describe the characteristics of patients with CKD (and at least one of the following: HF and/or T2DM)

who are treated with RAASi but do not achieve target dose. The maximum tolerated doses achieved by these patients and the length of time on these doses will be reported.

7. Aim and objectives

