7.2 Primary objective

1. To describe doses of RAASi prescribed to patients with CKD in the UK NHS setting

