9.5.1 Primary endpoint

The primary endpoint of this study is the mean maximum tolerated daily dose of RAASi achieved (as percentage of target dose).

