9.5.2 Secondary endpoints

The following endpoints will also be measured:

Prescribing modalities, including concomitant prescribing

- Length of time on maximum tolerated daily dose of RAASi
- Proportion of patients with HF who receive RAASi and MRA

- Maximum tolerated daily dose of MRA achieved in patients with HF
- Length of time on maximum tolerated daily dose of MRA in patients with HF
- Distribution of other drugs concomitantly prescribed for CKD and/or HF in patients treated with RAASi, by drug type

Clinical outcomes

- Proportion of patients with elevated serum potassium level (>5.1 mmol/L, >5.5 mmol/L or >6.0 mmol/L) during the observation period
- Number of episodes per patient with elevated serum potassium level (>5.1 mmol/L, >5.5 mmol/L or >6.0 mmol/L)
- Change in mean serum potassium level (from index date to last result during observation period)
- Change in mean serum creatinine level (from index date to last result during observation period)
- Change in mean urine protein level (from index date to last result during observation period)
- Change in mean blood pressure level (from index date to last result during observation period)
- Proportion of patients who stop RAASi treatment at least once during the observation period
- Reason(s) for changing RAASi dose or stopping RAASi treatment, where relevant

The following patient characteristics will also be included in analyses:

- Age at index event
- Sex
- Ethnicity
- HF status
- Comorbidities documented at baseline
- Length of time since diagnosis of CKD (and HF and/or T2DM, if relevant) at index event
- eGFR at baseline

- LVEF at baseline, if diagnosed with HF

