9.5.3 Variables to be collected

The variables to be collected in this study are shown in Table 2.

Table 2 Study variables

Data Item	Required detail	Time point(s)	Data source(s)
Date of birth	MM/YYYY	Index event	Hospital medical record
Gender	F, M	Index event	Hospital medical record
Ethnicity	Based on categories recommended by Office for National Statistics: White, Mixed / Multiple ethnic groups, Asian / Asian British, Black / African / Caribbean / Black British, Other ethnic group	Baseline	Hospital medical record
Date of CKD diagnosis	MM/YYYY	Baseline	Hospital medical record
Date of HF diagnosis, if relevant	MM/YYYY	Baseline	Hospital medical record
Date of T2DM diagnosis, if relevant	MM/YYYY	Baseline	Hospital medical record
Comorbidities	Based on diseases and conditions recorded in medical record	Baseline	Hospital medical record
eGFR	Date of observation, rate	Baseline until end of	Hospital medical records,

		observation period	including primary care correspondence
LVEF	Date of observation, ejection fraction	Baseline until end of observation period	Hospital medical records, including primary care correspondence
Serum potassium	Date of observation, level	Index date until end of observation period	Hospital medical records, including primary care correspondence
Serum creatinine	Date of observation, level	Index date until end of observation period	Hospital medical records, including primary care correspondence
Urine protein (albumin:creatinine ratio, ACR or protein:creatinine ratio, PCR)	Date of observation, level, type of test	Index date until end of observation period	Hospital medical records, including primary care correspondence
Blood pressure	Date of observation, level	Index date until end of observation period	Hospital medical records, including primary care correspondence
RAASi prescriptions	Drug name, dose, start date	Index date until end of observation	Hospital medical records, including

		period	primary care correspondence
MRA prescriptions, if relevant	Drug name, dose, start date	Index date until end of observation period	Hospital medical records, including primary care correspondence
Concomitant medications for CKD and/or HF	Drug name, start date	Index date until end of observation period	Hospital medical records, including primary care correspondence
Change in RAASi treatment	Date of change, reason for dose change/stopping of treatment	Index date until end of observation period	Hospital medical records, including primary care correspondence

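### The primary endpoint is labelled maximum tolerated dose but is defined as the highest dose recorded, so it cannot support conclusions about tolerability

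*Protocol*

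**What the plan says.** The protocol uses three different descriptions for what is meant to be one quantity.

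- **Definition (Section 3):** "Maximum tolerated dose: highest dose of RAASi (or MRA) recorded in medical records during observation period".
- **Endpoint (Section 9.5.1, repeated in the synopsis):** "The primary endpoint of this study is the mean maximum tolerated daily dose of RAASi achieved (as percentage of target dose").
- **Rationale (Section 6.1):** "the maximum tolerated doses that are currently achieved need to be determined".
- **Primary objective (Section 7.2):** "To describe doses of RAASi prescribed to patients with CKD in the UK NHS setting".

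Section 6 explains that target doses are often missed "due to clinician concerns about potential, or actual episodes of, hyperkalaemia". Section 9.5.2 lists "Proportion of patients who stop RAASi treatment at least once during the observation period" as a secondary endpoint, next to the reasons for dose changes or stops and the time spent on the maximum dose. For RAASi, Table 2 collects "Date of change, reason for dose change/stopping of treatment". For MRA, Table 2 collects drug name, dose and start date, but no reason for change. The limitations in Section 14 do not mention the definition.

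**The concern.** The definition takes the peak dose whatever happened next. A patient who is titrated up, found hyperkalaemic and then cut back or stopped is scored at the dose that was withdrawn. The protocol expects such patients: it names actual hyperkalaemia as a reason for missing target and makes stopping an endpoint in its own right. Yet nothing carries the stop, or its reason, back into the primary endpoint.

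What is at stake is the reading of the headline result. If the report says that patients tolerated on average some percentage of target, that statement will be too high whenever peak doses were withdrawn for intolerance. The secondary endpoint on time at the maximum dose has the same difficulty, since it mixes doses that were sustained with attempts that were abandoned. The MRA endpoints use the same definition.

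**Working it through.** **1. Inputs.** The definition, rationale, objective and endpoint come from Sections 3, 6.1, 7.2 and 9.5.1. The precision yardstick is Table 3 in Section 11. Two quantities are not in the protocol and are assumed: *f*, the share of patients whose peak dose was withdrawn for intolerance, and *d*, the average gap for them between peak dose and tolerated dose, in points of target.

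**2. One patient.** Recorded doses peak at 50% of target and are then cut to 25% for hyperkalaemia. The definition gives 50%. If treatment is stopped outright instead, it still gives 50%.

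**3. Direction.** Let A be all of a patient's recorded doses and T the subset not withdrawn for intolerance. Because T lies within A, max(A) ≥ max(T). If T is empty, any score set for that patient at or below the peak keeps the inequality. Averaged over the cohort, the error relative to the tolerated dose achieved is

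error in mean = f × d ≥ 0,

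and it is zero only if no peak dose was withdrawn for intolerance.

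**4. Yardstick.** Table 3 states no standard deviation, so one has to be back-solved. In the 50% row, an SD of 17 with mean ± 1.96 × SD/√n gives:

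- n=50: 1.96 × 17/√50 = 4.71, so 45.3 to 54.7 (table: 45 to 55)
- n=100: 1.96 × 17/√100 = 3.33, so 46.7 to 53.3 (table: 47 to 53)
- n=150: 1.96 × 17/√150 = 2.72, so 47.3 to 52.7 (table: 47 to 53)

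Any SD from about 16.2 to 17.9 reproduces that row. The printed half-widths at n=100 are 6 points (90% row), 5 (80%, 70% and 30% rows), 4 (60% and 40% rows) and 3 (50% row). Table 3 serves here only as a scale; this point disputes none of its figures.

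**5. Size under assumed values.**

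| f (assumed) | d (assumed) | f × d | Against Table 3 half-widths at n=100 |
|---|---|---|---|
| 5% | 25 | 1.25 | below every row |
| 10% | 25 | 2.5 | below every row |
| 20% | 25 | 5.0 | above at 60%, 50% and 40%; equal at 80%, 70% and 30%; below at 90% |
| 30% | 25 | 7.5 | above every row |

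**6. An error inside the half-width still matters.** With standard error SD/√100, SD from 15.3 to 18 (the 50% row, which is the tightest) and an error of b points, the chance that a nominal 95% interval covers the tolerated mean is Φ(1.96 − b/SE) − Φ(−1.96 − b/SE). This is 87% to 89% at b = 1.25, 63% to 72% at b = 2.5, and 10% to 21% at b = 5. A larger sample narrows the interval and leaves the error where it was.

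**The case against.** The strongest reply is that the primary objective speaks only of doses prescribed. The highest recorded dose answers that objective, and the definition is stated openly. This stands: for a highest-prescribed-dose endpoint there is no bias, and a reader who infers that the endpoint fails its own objective goes further than the protocol allows. What remains is the word tolerated in the endpoint name, and the rationale built on it.

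The net direction against true tolerability is also unknown. Section 6 says doses are held down by feared as well as actual hyperkalaemia, and patients held back by fear may tolerate more than they were ever given. The upward error shown above therefore applies only to the tolerated dose achieved by enrolled patients. Under-titration does not cancel that error; it is a second reason why the highest recorded dose is not a maximum tolerated dose.

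The secondary endpoints on time at maximum dose, stopping, reasons for change and raised potassium let a reader see part of the problem. They do not correct the primary mean.

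A reader might further infer that the same peak-dose rule decides who achieves target, so that patients who touched target and were cut back are excluded. The synopsis and Sections 9.2 and 9.2.1 do not say so. They require only that target was not achieved, without reference to the Section 3 definition. This is an ambiguity, and its effect on the mean has no known direction.

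**Conclusion.** The point holds as a mismatch between label and measurement. The objective says prescribed, the definition says highest recorded, and the endpoint name and rationale say tolerated. The mismatch is certain from the text and is not a detail left to the SAP, because the protocol fixes the definition itself.

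The direction, upward or zero, is certain only relative to the tolerated dose achieved by enrolled patients. The size is not known. The range of 1.25 to 7.5 points rests wholly on assumed shares of 5% to 30% and an assumed 25-point drop. It would be tempting to quote the upper part, 5 to 7.5 points, as the bias of the study; the protocol gives no figure that supports choosing it over the lower part.

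**What to change.** 1. **Rename.** Call the RAASi and MRA endpoints highest recorded dose wherever they appear, including the time-on-dose endpoints, and draw no conclusion about tolerability from them. Bring the rationale in Section 6.1 into line.
2. **Add one pre-specified RAASi analysis.** From the change dates and reasons in Table 2, identify peak doses reduced or stopped for recorded intolerance. Report the share of patients affected, and give the mean with those patients scored on a tolerability criterion that the sponsor and chief investigator set in advance. The criterion must state how outright stops and reasons marked as not known are scored. A rule that simply takes the highest dose not followed by a reduction or stop for intolerance would not do: read literally, it leaves no qualifying dose for a patient who stops outright, and it rejects a dose held for months before being lowered.
3. **MRA.** Table 2 holds no reason for change, so only the rename applies.
4. **Eligibility.** Leave it unchanged, since altering it would alter the study population. State whether briefly reaching target counts as achieving it.

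The cost is a wording amendment and a derivation from RAASi variables already collected. The analysis can be written into the SAP that Section 12 promises before data collection ends. The downside is that some reasons will be unrecorded, so the added analysis needs a sensitivity check, for example counting every unknown reason as intolerance and then none.
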